#### 6.2.4. Packaging

As defined in the protocol, the secondary endpoint for assessment of understanding and acceptability of the packaging by outpatients will be:

- Questionnaire on Day 0 (patients and/or caregivers):
  - Questions 1 to 8, separately
- Questionnaire on Day 11 (patients and/or caregivers):
  - Question 3: “Did you need help to take the treatment?”
  - Question 4: “Was the instruction manual (provided with the treatment) useful?”

#### 6.2.5. Pharmacokinetic (PK)

As defined in the protocol, the secondary endpoint for the PK assessment will be:

- PK parameters in whole blood, measured in all patients treated in hospital.

Statistical analyses of the PK parameters will be performed by [REDACTED]. These analyses will be defined in a separate statistical analysis plan, written by [REDACTED].

### 6.3. Safety endpoints

As defined in the protocol (Section 2.2.2), the secondary endpoints for the assessment of the safety of fexinidazole will be:

- Occurrence of grade  $\geq 3$  adverse events (AEs), including laboratory and haematological abnormalities (if considered clinically significant), between the first intake of fexinidazole and the end of the observation period\* or the follow-up period (18 months) for non-serious AEs assessed as related to fexinidazole.
- Occurrence of any serious adverse event (SAE) between the first intake of fexinidazole and the end of the follow-up period (18 months).
- Number of patients who prematurely discontinued treatment (i.e. prior to Day 10) or were hospitalised for reasons related to safety\*\* (e.g. including overdose).

\* The observation period extends from the first intake of fexinidazole on Day 1 until the end-of hospitalisation visit (between Day 13 and Day 18) for patients treated in hospital. For outpatients, the observation period extends to the end-of-treatment visit on Day 11.

\*\* A patient will be considered as “hospitalised for reasons related to safety” if he/she experienced a SAE during the treatment period and he/she was initially planned to be treated as an outpatient and he/she was hospitalized during the treatment period.

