6.8.2. Collection of Information on AEs

AEs may be observed directly by the medical personnel or spontaneously reported by the patient or his/her caregiver. For patients treated in hospital, potential AEs will be collected by the medical personnel each day during the treatment period and up to the EoH visit. The Investigator or qualified study personnel should examine any patient who experiences an AE as soon as possible. All medical measures necessary to ensure the patient's safety and well-being must be implemented. For patients treated on an out-patient basis, potential AEs that occur during the treatment period will be collected at the EoT visit, i.e. Day 11, or at any unscheduled visit to the centre between Day 1 and Day 11.

After the end of the periods mentioned above, AEs will be collected as described in Section 6.8.4.

Confidential Page 41 of 83

Information on AEs will be recorded in the corresponding section of the CRF using concise medical terms and avoiding vague, ambiguous or colloquial language. When a clinically significant laboratory abnormality is reported, whenever possible, a clinical diagnosis should be reported as the AE rather than simply an abnormal value, e.g. "anaemia" instead of "reduced red blood cell count".

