6.8.4. AE Collection Period

The collection period for AEs that occur in the context of the study is defined as follows:

- For any AE that is not considered to be an SAE: from the first intake of fexinidazole on Day 1 until the EoH visit (Day 13-18) for patients treated in hospital. For patients treated on an out-patient basis, the observation period extends to the EoT visit (Day 11).
- For **any SAE**: from the time of enrolment of the patient in the study (i.e. after signing the informed consent) and **until the end of follow-up** (18 months).

AEs that occur during the Screening period (after signing the informed consent) prior to the start of treatment and that are considered to be related (i.e. a reasonable possibility) to participation in the study, will also be collected by the medical personnel and recorded in the CRF.

In addition, any non-serious AE that occurs after the collection period and that the Investigator considers to be related (i.e. a reasonable possibility) to the IMP, must also be collected.

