#### Definition of treatment-emergent AEs:

Treatment-emergent AEs are defined as any AE which occurs on or after the date of the first study-drug administration until the end of the follow-up visit (i.e. 18-month visit).

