#### 8.8.2. Adverse events

Analysis of adverse events will be based on the concept of treatment-emergent adverse events (TEAE) (cf. definition in [Section 6.3.1](#)).

An overall summary of TEAEs occurring during the 18 months follow-up period (i.e. from first drug intake up-to end of follow-up) will be presented by cohorts, subgroups and overall. The following information will be tabulated (the number, percentage of patient and 95% CI):

- At least one TEAE
- At least one TEAE leading to treatment discontinuation (i.e. permanent or temporary)
- At least one TEAE leading to permanent treatment discontinuation
- At least one mild/moderate TEAE (grade 1, grade 2, mild or moderate)
- At least one severe TEAE (grade 3, grade 4, grade 5 or severe)
- At least one drug-related TEAE
- At least one serious TEAE
- At least one serious TEAE leading to treatment discontinuation (i.e. permanent or temporary)
- At least one serious TEAE leading to permanent treatment discontinuation
- At least one serious drug-related TEAE

For the following descriptions the number and percentage of patients and also the number of occurrences of TEAE will be presented by cohorts, subgroups and overall, and by MedDRA SOC and PT:

- TEAE
- Drug-related TEAE
- Serious TEAE
- Serious drug-related TEAE

All AEs and SAEs will be listed. In addition, TEAE leading to permanent or temporary treatment discontinuation and Drug-related TEAE which occurred during the treatment period (i.e. between the first study-drug intake (included) and the last study-drug intake (included)) will be listed (cf. [Section 9.1](#)).

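### For non-serious, unrelated AEs the in-patient and out-patient columns cover different collection windows, and SAP 8.8.2 sets no common cut-off

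*SAP*

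**What the plan says.** Protocol 6.8.4 collects non-serious AEs from first intake "until the EoH visit (Day 13-18) for patients treated in hospital". SAP 6.3 repeats the split by setting: "For outpatients, the observation period extends to the end-of-treatment visit on Day 11". Protocol Table 2 lets the out-patient end-of-treatment (EoT) visit fall one day later, on Day 12.

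Two kinds of event escape the split. SAEs are collected to 18 months in both cohorts. Protocol 6.8.4 also keeps, in both cohorts, "any non-serious AE that occurs after the collection period and that the Investigator considers to be related" to the study drug.

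The way events are found differs too. Protocol 6.8.2 has staff collect AEs daily from hospitalised patients. For out-patients, "potential AEs that occur during the treatment period will be collected at the EoT visit", or at any unscheduled visit between Day 1 and Day 11.

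SAP 6.3.1 defines a treatment-emergent AE (TEAE) as "any AE which occurs on or after the date of the first study-drug administration until the end of the follow-up visit" at 18 months. Under SAP 8.8.2 the overall summary, described as covering the 18-month follow-up, "will be presented by cohorts, subgroups and overall", with number, percentage and 95% CI. The templates in SAP 9.2.9 and 9.2.10 put in-patients and out-patients side by side. The only restriction to the treatment period is a listing of drug-related TEAEs.

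**The concern.** A reader of these tables sees two adjacent columns under an 18-month label and will take them to cover the same period. For non-serious events judged unrelated, they do not: in-patients have two to seven more days of collection (one to six if the out-patient visit falls on Day 12). Nothing in the SAP aligns the windows, adjusts for time at risk or warns of the difference at the table.

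The study is meant partly to support treatment outside hospital (Protocol 1.6), so these columns will be read against each other whether or not a test is planned. Where the window matters, it acts in one direction: it makes the hospital column look worse and the home column better.

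**Working it through.** **Which outputs are affected.** SAP 8.8.2 lists ten summary rows and four SOC/PT tables.

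- *Affected (three rows):* any TEAE; mild/moderate TEAE; severe (grade 3 or above) TEAE, for its non-serious unrelated part only.
- *Not affected (three rows):* drug-related, serious, and serious drug-related TEAE. These are collected to 18 months in both cohorts.
- *Essentially not affected (four rows):* the discontinuation rows. They concern dosing days, which both windows cover.
- *SOC/PT tables:* only the all-TEAE table is affected.

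**Window length.** In-patients: 13 to 18 days. Out-patients: 11 days, or 12 with the leeway.

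- 13/11 = 1.18 and 18/11 = 1.64.
- 13/12 = 1.08 and 18/12 = 1.50.

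**Direction.** Extra days of collection cannot remove a patient who already has an event. In the affected rows the longer window can therefore leave the in-patient percentage unchanged or raise it, but cannot lower it.

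**Size.** The plan states no AE rate, so it has no figure of its own to reproduce. Two quantities must be assumed: the proportion p with an affected AE (non-serious, unrelated) by Day 11, and f, the hazard after Day 11 relative to the hazard before it. Underlying risk is taken as equal in the two cohorts.

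- Daily hazard: h = −ln(1 − p)/11.
- In-patient proportion with EoH on day T: 1 − exp{−h × [11 + f × (T − 11)]}.
- For p = 0.30: h = 0.3567/11 = 0.0324.
- f = 1, T = 18: 1 − exp(−0.0324 × 18) = 44.2%.
- f = 0.25, T = 18: 1 − exp(−0.0324 × 12.75) = 33.9%.

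| Out-patients by Day 11 | f = 0 | f = 0.25, EoH Day 13 to 18 | f = 1, EoH Day 13 to 18 |
|---|---|---|---|
| 30% | 30.0% | 31.1% to 33.9% | 34.4% to 44.2% |
| 50% | 50.0% | 51.6% to 55.2% | 55.9% to 67.8% |

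The f = 1 column is the upper end of the range shown. These figures apply to affected AEs only; the whole AE rate should not be scaled this way, because serious and related events after Day 11 are collected in out-patients as well.

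**After a cut at Day 11 in both cohorts,** the window ratio is 11/11 = 1.00 and the artefact from window length is zero.

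**The case against.** The case for leaving the plan alone has several sound parts.

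- No contrast between cohorts is planned. The tables are descriptive, and SAP 6.3 states the unequal windows openly.
- The rows that say most about drug safety, serious and drug-related, are untouched.
- Dosing ends on Day 10, and laboratory tests and ECG fall on Day 11 in both cohorts, with none scheduled at the EoH visit. Few new events may arise in the extra days, and the artefact could be close to zero.
- Out-patients who are hospitalised follow in-patient procedures to the end of hospitalisation but stay in the out-patient column (Protocol 6.5, SAP 5), a partial offset.
- Daily questioning against interview, and the selection of out-patients with Karnofsky status above 50%, no neurological symptoms and no pregnancy or breastfeeding (Protocol 4.3), separate the cohorts in ways that no cut-off removes.

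All of this limits the point. None of it explains why one removable difference should remain in the tables under a label that hides it.

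Two stronger readings are tempting and should be resisted. A reader might infer that hospital-versus-home safety is itself an objective; Protocol 2.1.2 covers safety in both settings without setting one against the other. A reader might also infer that in-patients are bound to look less safe across all AE rates; most rows share a window, and the documents give no event rate after Day 11 from which to conclude it.

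**Conclusion.** The point holds for three summary rows and one SOC/PT table. In these, following the plan can raise the in-patient percentage purely through longer collection. Starting from an assumed 30% by Day 11, the excess runs from 0 points (no hazard after Day 11) through 1.1 to 3.9 points (a quarter of the earlier hazard) to 4.4 to 14.2 points (constant hazard). This rests on equal underlying risk and an out-patient visit on Day 11; a Day 12 visit shortens the difference. It is a presentational weakness in the descriptive safety tables, cheap to mend, and does not touch the serious or drug-related results.

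**What to change.** In SAP 8.8.2:

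1. Add a by-cohort version of the three affected rows and of the all-TEAE SOC/PT table, limited to AEs with onset from Day 1 to Day 11 in both cohorts.
2. Report in-patient AEs with onset from Day 12 to the EoH visit separately.
3. Keep the full-window tables as planned.
4. Footnote the by-cohort AE tables with the collection windows, the difference in ascertainment (daily questioning against the Day 11 interview or unscheduled visits) and the non-random allocation to hospital or home. State that the columns are descriptive and that the Day 11 cut does not make the cohorts comparable.

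No new data are needed: onset dates are collected, and SAP 7.6 already has imputation rules for them. Those rules move missing dates early, so the number of imputed onsets falling in the Day 1 to Day 11 table should be stated. SAP 11 already records post-lock changes, so a late addition can be labelled in the same way.

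The cost is one extra table, which omits in-patient events after Day 11 from that table only.

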2.2.2. Secondary Endpoints - Safety

The secondary endpoints for the assessment of the safety of fexinidazole will be:

- Occurrence of grade ≥ 3 adverse events (AEs), including laboratory and haematological abnormalities (if considered clinically significant), between the first intake of fexinidazole and the end of the observation period* or the follow-up period (18 months) for non-serious AEs assessed as related to fexinidazole. AE severity will be graded according to the National Cancer Institute (NCI) Common Toxicity Criteria for AEs (CTCAE), Version 4.03 (12) and, for certain laboratory parameters, modified CTCAE will be used.
- Occurrence of any serious adverse event (SAE) between the first intake of fexinidazole and the end of the follow-up period (18 months).
- Number of patients who discontinued treatment or were hospitalised during treatment for reasons related to safety, including overdose.
 - *The observation period extends from the first intake of fexinidazole on Day 1 until the end-of-hospitalisation visit (between Day 13 and Day 18) for patients treated in hospital. For out-patients, the observation period extends to the end-of-treatment visit on Day 11.

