6.5. Treatment Period for Patients Treated on an Out-patient Basis

Patients treated on an out-patient basis who require hospitalisation, for whatever reason, will undergo the same procedures as patients initially treated in hospital, up to the end of the hospitalisation period, as provided for in the protocol. During this period, and up to Day 13 or Day 18, the reasons for hospitalisation will not be considered to be SAEs solely based on the criterion of hospitalisation, but may be considered to be SAEs based on other criteria (see Section 6.8.1).

PK sampling should be performed at any unscheduled visit between Day 1 and Day 10, regardless of the day on which the visit takes place.

Confidential Page 36 of 83

6.6. Procedures at the EoT Visit – Day 11

Whether the patient is being treated in hospital or as an out-patient, the following procedures will be performed at the EoT visit on Day 11:

- Collection of blood and/or lymph samples for testing for parasites;
- Collection of signs and symptoms of HAT, if any;
- Karnofsky Performance Status;
- Vital signs: body temperature, blood pressure, heart rate and respiratory rate;
- Physical and neurological examinations;
- Collection of concomitant medication and AEs;
- Urine pregnancy test for women of child-bearing potential;
- Laboratory safety assessments (see Appendix 3 Laboratory Tests; p 75) when possible, samples will be collected in the morning from patients in the fasting state;
 - Haemoglobin;
 - Haematology: WBC, platelet count;
 - o Biochemistry: albumin, ALP, ALT, AST, BUN, chloride, creatinine, glucose, potassium, sodium, calcium, total bilirubin, bicarbonates and total protein;
 - Urine analysis (leucocytes, nitrites, pH, protein, glucose, ketone bodies, urobilinogen, bilirubin, blood and haemoglobin);
- Triplicate digital ECG (CarTouch®);
- Collection of blood sample 24 hours after the last intake of the IMP (Day 11) for PK analyses. If the patient was treated on an out-patient basis, the sample will be used to check treatment compliance. If the patient was treated in hospital, a second blood sample will be collected 48 hours (Day 12) after the last intake of the IMP for PK analyses.

Table 4 - PK Sampling Times at the End of the Treatment Period

Ideal timing for sample collection	Acceptable leeway
Day 11: 24 hours after the last intake of the IMP	± 1 hour
Day 12: 48 hours after the last intake of the IMP (only for patients treated in hospital)	± 1 hour

Confidential Page 37 of 83

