(e.g. cosmetic surgery) or in the context of usual management of the disease (including treatment adjustment) will not be considered as an SAE. Similarly, hospitalisation of patients initially treated on an out-patient basis will not be considered as an SAE solely based on the criterion of hospitalisation because, in accordance with Section 6.5, they are to remain in hospital, as are patients initially hospitalised, up to Day 13 or 18. The other seriousness criteria remain valid. This includes hospitalisation for reasons related to non-compliance with treatment, including for a non-serious AE based on the other seriousness criteria;

- results in persistent or significant disability or incapacity;
 - i.e. an AE that leads to significant impairment of the patient's ability to carry out normal activities;
- is a congenital anomaly or birth defect in the child or foetus of a female patient exposed to treatment prior to conception or during pregnancy;
- is an important medical event, i.e. an event that may not be immediately lifethreatening or result in death, but that jeopardises the patient's safety or requires an intervention to prevent one of the outcomes above.

In the study, ALT or AST levels above 3 ULN associated with total bilirubin above 2 ULN will be considered to be SAEs.

Any suspected transmission of an infectious agent via the IMP will also be considered as an SAE.

Any other event defined as serious in the protocol will be reported as an AE and as an SAE in accordance with the procedure described in Section 6.8.5.

For the purposes of the study, hospitalisation for non-complicated delivery will not be considered as an SAE.

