9.6. Secondary Analyses

9.6.1. Secondary Analysis - Safety

The secondary safety analyses will be performed on the mITT population, i.e. all patients who took at least one tablet of fexinidazole.

The proportion of patients who experienced an SAE and/or an AE leading to treatment discontinuation will be described by system-organ class using Medical Dictionary for Regulatory Affairs (MedDRA) terms and/or NCI CTCAE, version 4.03 (14) and, for certain laboratory parameters, modified CTCAE will be used (see Appendix 6 – CTCAE v4.03 adapted, p 81).

The proportion of patients who experienced at least one AE will be described. Events described using the same term and that occur several times in the same patient will be counted only once. If a patient experiences several events described with the same term, the event with the maximal severity will be included in the analysis. In addition, each SAE will be described in a narrative presenting all aspects of the medical event and the causality assessment.

The incidence of AEs and of SAEs and their respective 95% confidence intervals will be presented by category and by frequency. In other cases, only descriptive statistics will be presented.

Laboratory safety parameters, i.e. haematology and biochemistry, will also be described individually, indicating the proportions of patients by category corresponding to the size of the increase in relation to the ULN for liver function tests (< 1 ULN, 1–2 ULN, 2–3 ULN etc.). Scatter graphs with baseline values on the x-axis and post-treatment values on the y-axis with the bisector indicating the absence of change will be presented. Changes in blood levels over time will be presented in graphs. Shift tables will be provided to supplement signal detection. A listing of patients with clinically significant increases in laboratory parameters will be provided.

Confidential Page 50 of 83

Abnormalities, if any, on ECG tracings recorded on Day 11 will be described.

The proportion of patients hospitalised for a safety problem, including overdose, will also be presented.

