#### Clarifications:

Only laboratory and haematological abnormalities reported as AEs by investigators (cf. Section 6.8.1 of the protocol for further details) will be analyzed as AEs.

Additional secondary safety endpoints are defined in this SAP (cf. sections 6.3.1, 6.3.2 and 6.3.4).

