### 6.3.4. Other safety endpoints

- Number of patients who discontinued treatment for safety reason\*,

DNDi-FEX-09-HAT (DNDi)	Statistical Analysis Plan Version 3.0 – 30/09/2022	Page 12 / 37
------------------------	---	--------------

- Number of patients who were hospitalized for reasons related to safety\*, including overdose.

\* Reasons collected in the CRF comments will be classified by a medical review as "safety reason" or "other reason".

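### SAP 6.3 decides whether an out-patient's hospitalisation was safety-related by whether an SAE occurred, not by the reason for admission, and SAP 6.2.3 drops the non-compliance hospitalisation count

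*SAP*

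**What the plan says.** **Safety.** Protocol 2.2.2 has as a secondary safety endpoint: "Number of patients who discontinued treatment or were hospitalised during treatment for reasons related to safety, including overdose". Protocol 9.6.1 adds: "The proportion of patients hospitalised for a safety problem, including overdose, will also be presented". Neither requires the event to be serious.

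SAP 6.3 opens with "As defined in the protocol (Section 2.2.2), the secondary endpoints for the assessment of the safety of fexinidazole will be" and repeats the endpoint, still naming overdose. A footnote then gives the working rule. A patient counts as hospitalised on safety grounds "if he/she experienced a SAE during the treatment period and he/she was initially planned to be treated as an outpatient", with the further condition of admission during the treatment period.

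The clarifications to SAP 6.3 say: "Additional secondary safety endpoints are defined in this SAP". One of these, in SAP 6.3.4, is again the number hospitalised on safety grounds including overdose, decided differently: "Reasons collected in the CRF comments will be classified by a medical review as" either safety or other. SAP 8.8.1 analyses the 6.3 endpoint and SAP 8.8.5 the 6.3.4 endpoints. The list of tables in SAP 9.1 names no table for either.

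**What makes an out-patient admission an SAE.** Protocol 6.5 says that the reasons for admitting an out-patient "will not be considered to be SAEs solely based on the criterion of hospitalisation, but may be considered to be SAEs based on other criteria". Protocol 6.8.1 repeats the rule and continues: "This includes hospitalisation for reasons related to non-compliance with treatment, including for a non-serious AE based on the other seriousness criteria".

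**Feasibility.** Protocol 2.2.4 and 9.6.3 count out-patients hospitalised because of non-compliance; 9.6.3 asks for the proportion with a 95% CI, and 9.3 lists the same group under disposition. SAP 6.2.3, also introduced as following the protocol, counts any hospitalisation in the treatment period and puts the reasons in a listing. SAP 8.7.4 gives 95% CIs for the 6.2.3 endpoints only.

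**Changes and versions.** SAP Section 11 lists three changes: adverse event counting, removal of interim analyses, and a correction to the outcome algorithm after database lock. Neither hospitalisation item is among them. SAP Section 4 cites protocol version 2.0; the protocol supplied is version 3.0.

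**The concern.** The protocol endpoint depends on why the patient was admitted. The footnote depends on whether an SAE occurred in the same period, with no link required between the two. Because the protocol says that admitting an out-patient does not by itself make the event serious, the two conditions can diverge in either direction.

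The report could then carry two different numbers under nearly the same label. The one presented as the protocol endpoint would be the one that departs from it. The safety and feasibility of out-patient treatment are stated secondary objectives, and confirming that treatment outside hospital is feasible is part of the rationale in protocol 1.6. A count of admissions by reason bears directly on both.

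**Working it through.** The plan gives no figure for this point, so there is none to reproduce. The check compares the definitions case by case.

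**Step 1: classify out-patient admissions during the treatment period.** I read the footnote as a definition, and assume that the medical review assigns reasons correctly.

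| Class | Reason for admission | SAE in period | Protocol 2.2.2 | SAP 6.3 footnote | SAP 6.3.4 review |
|---|---|---|---|---|---|
| A | Safety | Yes | Counted | Counted | Counted |
| B | Safety | No | Counted | Missed | Counted |
| C | Other | Yes | Not counted | Counted | Not counted |
| D | Other | No | Not counted | Not counted | Not counted |

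**Step 2: size of the discrepancy.**

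- Protocol count = A + B.
- Footnote count = A + C.
- Error = (A + C) − (A + B) = C − B.
- Lower limit: if A = 0 and C = 0, the error is −B, so every safety admission is missed.
- Upper limit: if B = 0 and D = 0, the error is +C, so every other-reason admission is counted.
- The footnote picks out the right patients only if B = C = 0. If B = C but both are above zero, the total is right and the patients are wrong.

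The documents give no admission or SAE frequencies, so neither the sign nor the size of C − B can be computed.

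**Step 3: weight of one net miscounted patient.** The planned sample is 174. If all are treated, the step in the overall proportion is 1/174 = 0.57 percentage points. The out-patient share is not stated. At assumed shares, the step in the out-patient column is:

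- 25%: 1/(0.25 × 174) = 1/43.5 = 2.30 points
- 50%: 1/(0.50 × 174) = 1/87 = 1.15 points
- 75%: 1/(0.75 × 174) = 1/130.5 = 0.77 points

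This concerns the hospitalisation part only. The 6.3 endpoint also counts treatment discontinuation, and a patient already counted that way does not change the combined number.

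**Step 4: the conflict inside the SAP.** An overdose that leads to admission without an SAE falls in class B. The endpoint wording in SAP 6.3 and 8.8.1 includes it, the footnote excludes it, and SAP 6.3.4 includes it. This holds whatever the protocol version.

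**Step 5: feasibility.** Let N be the out-patients admitted because of non-compliance. The protocol count is N. The SAP 6.2.3 count is A + B + C + D, of which N is a subset, so it can only equal or exceed N. The disposition summary in SAP 8.1 does not restore N.

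**The case against.** **Version.** The SAP works from protocol 2.0, and its source text evidently differs from version 3.0: SAP Section 11 says interim analyses were planned in protocol 9.7, whereas that section in version 3.0 plans none. This stands. A reader might infer that the SAP misdescribes its own source, or that a change was knowingly left out of Section 11. The documents do not support that, because the version 2.0 wording cannot be seen. What can be shown is that the SAP does not match version 3.0 and, separately, that it conflicts with itself.

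**The right count is already planned.** SAP 6.3.4 has no SAE condition and is analysed by cohort, by subgroup and overall. This also stands. A reader might infer that safety admissions will go unreported or that safety will look better than it is. Neither follows: 6.3.4 can capture what the footnote misses, and the net error may go either way. What remains is that the sound count is labelled additional while the unsound one carries the protocol's name.

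**Weak textual support.** The sentence in protocol 6.8.1 that mentions a non-serious AE is garbled and attaches it to non-compliance. It is poor evidence that such safety admissions are expected. The mechanism does not need it; the rule in protocol 6.5 is enough to make class B possible. Nothing in the documents shows that class B or class C is common.

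**Feasibility is recoverable.** The listing of reasons may let a reader identify non-compliance admissions. That is fair. The loss is one descriptive proportion with its CI, not the underlying data.

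**Conclusion.** The footnote is wrong as written for the endpoint it serves. It contradicts protocol 3.0, the SAP's own reference to overdose, and SAP 6.3.4. Following it can give a wrong count for the hospitalisation part of a named secondary safety endpoint, by C − B patients, with sign and size unknown. SAP 6.2.3 separately omits a proportion and CI that protocol 3.0 plans.

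Both endpoints are descriptive and secondary, and the primary success rate is untouched. The statements about labelling and about Section 11 are made against version 3.0 only. The percentage-point steps assume 174 treated patients and, for out-patients, the assumed shares shown. The point merits correction because the remedy is small and largely planned already, not because a large effect has been shown.

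**What to change.** 1. In SAP 6.3, replace the footnote with the medical-review classification of SAP 6.3.4, irrespective of seriousness and including overdose. State in SAP 8.8.1 that this rule applies.
2. Keep the SAE-based count, if wanted, as a supplementary count with its own label: out-patients admitted who had an SAE in the treatment period.
3. In SAP 6.2.3, report non-compliance admissions with a 95% CI beside the any-reason count, using the reasons already collected, with a not-determinable category where they are insufficient.
4. Update the protocol version cited in SAP Section 4, and record both items in Section 11 as departures from the current protocol, with their timing relative to database lock.

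The cost is SAP wording and a small amount of extra coding in a review that is planned with two categories, safety and other. The CRF is not among the documents, so whether its comments support a non-compliance category must be checked first. The downside is a change to a descriptive secondary endpoint after database lock in an open-label study. It should be disclosed as such; showing both safety counts side by side lets readers see its effect.
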